Document Cover Page

Official Title of the Study: A randomized clinical trial of single dose liposomal bupivacaine delivered via VATS intercostal nerve block vs continuous bupivacaine infusion delivered via indwelling subscapular analgesic catheter in patients undergoing surgical stabilization of rib fractures

NCT Number: NCT03305666

Date of Document: April 27, 2017

COMIRB Protocol

COLORADO MULTIPLE INSTITUTIONAL REVIEW BOARD
[name] [contact] [contact]

Protocol #: 17-0685

Project Title: A randomized clinical trial of single dose liposomal bupivacaine delivered via VATS intercostal nerve block vs continuous bupivacaine infusion delivered via indwelling subscapular analgesic catheter in patients undergoing surgical stabilization of rib fractures

Principal Investigator: [name] MD

Version Date: V1 4/27/2017

I. Hypotheses and Specific Aims:

The hypothesis of this clinical trial is that among patients undergoing surgical stabilization of rib fractures (SSRF), liposomal bupivacaine delivered via VATS intercostal nerve block provides comparable analgesia to the pain catheter, as measured by both pulmonary function and narcotic use.

II. Background and Significance:

Rib fractures represent a common injury pattern with high associated morbidity and mortality (1). Effective pain control in both the acute and long term periods remains a challenge (2). Surgical stabilization of rib fractures (SSRF) is now a recommended treatment for patients with severe chest wall injuries (3-5). In addition to stabilization of the chest wall, SSRF offers a unique opportunity to deliver directed, loco-regional anesthesia. Loco-regional anesthesia is a recognized, essential component of multi-modal anesthesia for patients with rib fractures in order to both decrease pain and minimize the use of opioids and their associated side effects (6, 7).

Delivery options for loco-regional anesthesia to patients with rib fractures share in common the intention of anesthetizing the intercostal nerves. Moving from the spinal cord distally, modalities include thoracic epidural catheters, paravertebral blocks or catheters, and rib blocks. Although rib blocks may be accomplished via a variety of techniques, the two most common intra-operative techniques are video-assisted thoracoscopic surgery (VATS) intercostal nerve blocks [Figure 1] and indwelling, subscapular catheters (Figure 2).

In general, neuraxial modalities such as thoracic epidural and para-vertebral injections/catheters are subject to a wide array of limitations, including patient coagulopathy (Internal Normalized Ratio > 1.5), co-existing spine fractures, peri-insertion and removal holding of venous thromboembolism pharmacoprophylaxis, and provider availability. For these reasons, our current practice is to insert a subscapular “pain catheter” at the conclusion of the SSRF operation (Figure 2); this catheter provides a continuous infusion of 0.25% bupivacaine and may be left in place for several days.

Although favorable results using the pain catheter have been published in patients with rib fractures who have not undergone SSRF (8), we have noticed several limitations to this treatment modality. First, position is highly variable; and, because the catheter is not truly in the space of the intercostal nerves (Figure 3), drug delivery is likely irregular. This variability may be particularly relevant in obese patients; and the median body mass index of patient who underwent SSRF at Denver Health is 29 kg/m². Beyond catheter placement, we have also experienced issues with leakage of drug from the skin entry site of the catheter. Moreover, catheters frequently become dislodged or inadvertently removed during patient transport. Further, the indwelling foreign body likely introduces some risk of infection. Finally, the presence of the catheter is distressing to many patients.

Liposomal bupivacaine (Exparel, Pacira Pharmaceuticals, Inc., Parsippany, NJ, www.pacira.com) provides sustained analgesia for up to 72 hours following a single injection of the drug delivery system. The safety and efficacy of liposomal bupivacaine has been evaluated

in over 1,300 subjects and 21 clinical trials (refs from pamphlet). Although many of these trials have included thoracic surgery patients (9-11), no trial has evaluated the efficacy and safety of liposomal bupivacaine administered to patients with rib fractures undergoing SSRF. Potential benefits as compared to current practice include directed injection into the intercostal nerve space using a VATS approach, as well as obviation of the need for an indwelling catheter. The hypothesis of the current clinical trial is that, among patients undergoing SSRF, liposomal bupivacaine delivered via VATS intercostal nerve block provides comparable analgesia to the pain catheter, as measured by both pulmonary function and narcotic use.

III. Preliminary Studies/Progress Report:

Although SSRF is now a recognized treatment for patients with severe chest wall injuries, the method of loco-regional anesthesia is less standardized. Currently thoracic epidural and paravertebral catheters are both common methods for delivering loco-regional anesthesia. Thoracic epidural catheters offer the benefit of bilateral analgesia and have been shown to reduce the length of mechanical ventilation (3). Unfortunately they are contra-indicated in the setting of spine fractures and mild coagulopathy, and may require the addition of a consultative service to manage. Paravertebral pain catheters have equivalent pain control to epidural catheters, but can be used in patients with spine fractures and can be placed surgically or by emergency teams using anatomic landmarks or ultrasound guidance (3). Denver health has found that these catheters are not without issues for our patients. Some issues that we have personally experienced include drug leakage, dislodgement, and irregular drug delivery. Other pain loco-regional analgesic modalities such as intrapleural pain catheters, transcutaneous patches, transcutaneous electrical nerve stimulation, and acupuncture have limited evidence to support their use (3). While still a relatively new technique for loco-regional anesthesia, liposomal bupivacaine has shown favorable results in patients undergoing thoracoscopies and thoracotomies, resulting in shorter hospital length of stay (11) and statistically significant additional analgesics (10). The ease of delivery of liposomal bupivacaine and the ability to avoid bothersome catheters may make it the optimal method for loco-regional anesthesia in patients undergoing SSRF.

IV. Research Methods

A. Outcome Measure(s):

Individuals undergoing SSRF will be randomized to two treatment arms. Primary outcomes will be pulmonary function and narcotic requirement by each subject.

Pulmonary function will be measured using the Standardized Assessment of Respiratory Function (SCARF) score, measured at 10 am daily. This scale has 4 components, and one point award for each of the following:

- 1) Numeric Pain score >4 (on the 10 point pain scale)
- 2) Incentive spirometry <50% predicted
- 3) Poor cough
- 4) Respiratory rate ≥ 20

Daily Narcotic use will be measured using equi-analgesic doses as shown in the table below.

Narcotic	Dose	Unit	Route
Hydromorphone	1.5	Mg	IV
Hydromorphone	7.5	Mg	PO
Fentanyl	100	Mcg	IV
Morphine	10	Mg	IV
Morphine	30	Mg	PO
Oxycodone (Percocet)	20	Mg	PO
Hydrocodone (Vicodin)	30	Mg	PO

B. Description of Population to be Enrolled:

Adults undergoing surgical stabilization for rib fractures are eligible for this clinical trial. Any individuals that are pregnant, incarcerated, less than 18 years old, or have a known allergy or hypersensitivity to bupivacaine will not be eligible for enrollment.

C. Study Design and Research Methods

This is a non-inferiority, randomized clinical trial that compares two different delivery options for loco-regional anesthesia for patients undergoing surgical stabilization of rib fractures. Randomization will be accomplished using a standard function in Microsoft Excel that randomly chooses either the number 0 or 1.

Prior to patient's SSRF procedure they will be localized to one of two study arms:

- 1) Pain Catheter: placed in the subscapular space at the time of surgery and results in a continuous infusion of 12ml/hr of 0.25 bupivacaine and is left in place for a maximum of 120 hours.
- 2) Single injection liposomal bupivacaine: a mixture of 20mL liposomal bupivacaine, 20 mL 0.25% bupivacaine, and 10mL sterile saline (50mL total) that is delivered into the intercostal space during VATS using a 22 gauge needle directed at ribs 3 through 8. (178mm????)

The SSRF procedure will be standardized for all patients to include: 1) flexible bronchoscopy, 2) E-Z Blocker bronchial blocker (figure 5), and 3) VATS evacuation/irrigation of the pleural space.

Postoperatively, standard multimodal analgesia will be used in all patients (barring any contra-indications) to include: 1) Acetominophen 650 mg PO q6H, 2) Ibuprophen 800 mg PO q6h, and 3) Gabapentin 300 mg PO TID

Subjects will be followed for 28 days or until discharged from the hospital, whichever comes first. Crossover from one study arm to the other will not be permitted. Patients in whom pain is not well controlled postoperatively will be given additional analgesics other than bupivacaine.

Occasionally patients with rib fractures receive a pain catheter placed prior to surgery using anatomic landmarks. For these patients the presence of a pre-existing pain catheter will be noted in the data collection sheet. Patient's with a pre-existing pain catheter will have it removed at the time of SSRF. Depending on randomization status, the patient will receive either a new pain catheter placed intra-operatively and under direct vision, or liposomal bupivacaine administered via VATS intercostal nerve block.

D. Description, Risks and Justification of Procedures and Data Collection Tools:

On October 28th 2011, the Food and Drug Administration approved liposomal bupivacaine for the following indication: "administration into the surgical site to produce postsurgical analgesia".

This study will be conducted and reported in accordance with the recommendations of the Consolidated Standards of Reporting Trials Statement (14) and registered with the U.S. National Institutes of Health (clinicaltrials.gov). An independent study monitor ([name], Pharm D) will submit written reports to COMIRB every six months. Adverse events will be recorded and reported to both the data safety monitor and COMIRB.

E. Potential Scientific Problems:

This is a randomized, clinical trial, however, due to the nature of the two treatment arms this study is not blinded. Clinical providers, patients, and the research coordinator collecting data will know which treatment arm the patient is assigned to. This study is subject to the Hawthorne Effect in which the patients may modify their behavior while being observed. Specifically, patients may exaggerate or downplay their pain level while being enrolled. Reported pain, especially on the 10-point pain scale is also highly subjective and will be a limitation in this study. The SCARF

score also incorporates other variables, such as respiratory rate and incentive spirometry volumes which are less subject measures. These will help mitigate the subjectivity of self-reported pain scores.

F. Data Analysis Plan:

Inferiority of liposomal bupivacaine as compared to pain catheter will be defined as median daily SCARF score one point higher. Standard deviation of the SCARF score among patients with rib fractures in Denver Health surgical intensive care unit is 1.1. Using beta = 0.80 and alpha = .05, this returns a total sample size of 34 subjects. Twenty-four SSRF procedures are performed annually at Denver Health, thus we conclude that the trial is feasible and may be completed in 1.5 years.

A standard data collection tool will be used (see Data Collection Tool). All statistical analysis will be conducted using SAS version 9.4 (SAS Inc., Carey, NC). Statistical significance will be defined as $p < .05$. The distribution of continuous variable will be accessed for normality using the Kolmogorov-Smirnov test. Normally distributed continuous variables will be compared using the student's t-test. Non-normally distributed variables will be compared using the Wilcoxon Rank test. Categorical variables will be compared using chi-squared test, unless expected cell counts were <10 , in which case Fischer's exact test will be used.

G. Summarize Knowledge to be Gained:

Rib fractures are common and associated with both acute and chronic pain. This trial will compare two loco-regional treatment modalities currently in use at Denver health to determine the optimal method to decrease post-operative pain and minimize opioid use. Denver Health is a leader in trauma care, including rib fractures. Our team has been produced multiple peer reviewed studies detailing current recommendations for treatment of rib fractures. We will continue to explore novel approaches for trauma patients suffering from rib fracture pain control to further improve patient outcomes and patient satisfaction.

H. References:

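### Narcotic use is one of two primary outcomes in a non-inferiority claim on both, but the margin, SD and N = 34 are for SCARF only, so narcotic use has no success rule and 80% power is not established for the joint claim

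*Combined protocol and SAP*

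**What the plan says.** Section IV.A (Outcome Measures) names two primary outcomes and does not rank them: "Primary outcomes will be pulmonary function and narcotic requirement by each subject". The first is scored daily: "Pulmonary function will be measured using the Standardized Assessment of Respiratory Function (SCARF) score, measured at 10 am daily". The second has a conversion table: "Daily Narcotic use will be measured using equi-analgesic doses as shown in the table below".

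Sections I and II give the hypothesis in the same conjunctive form, that the liposomal block "provides comparable analgesia to the pain catheter, as measured by both pulmonary function and narcotic use". Section IV.C sets the design: "This is a non-inferiority, randomized clinical trial that compares two different delivery options for loco-regional anesthesia".

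Section IV.F (Data Analysis Plan) has one decision criterion: "Inferiority of liposomal bupivacaine as compared to pain catheter will be defined as median daily SCARF score one point higher". It adds a SCARF SD of 1.1 and an alpha of .05 with no sidedness. It prints beta as 0.80, evidently meaning power, and arrives at 34 subjects in total. For narcotic use it gives no margin, SD, power or decision rule. Its general test list sends continuous variables to the t-test or the Wilcoxon test, with significance at p < .05.

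**The concern.** A non-inferiority claim needs a margin for every outcome on which it rests. Here one of the two has none. A difference test on narcotic use can end in two ways. If significant, it shows that the arms differ. If not significant, it shows only that a difference was not detected, and with 34 patients that is weak evidence of comparability. The plan does not say how such a result would be read.

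Two things are at stake. First, half of the stated hypothesis cannot be confirmed by the plan as written. A margin or reading rule chosen later, in a trial that section IV.E says is unblinded, would depend on the data. Second, a reader will take the stated power as the chance of supporting the whole hypothesis, when it was derived for one component.

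**Working it through.** **Inputs.** From section IV.F: SCARF margin 1, SD 1.1, power 0.80, alpha .05, total N 34. Assumed, because not stated: equal arms (34/2 = 17; section IV.C describes a simple 0-or-1 draw), true differences of 0, no dropout. Narcotic margin, SD and correlation with SCARF: not given, so varied below.

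**1. Reproduce the 34.** Non-inferiority on means, per arm n = 2(SD/margin)²(z₁₋α + z₀.₈₀)².
- One-sided .05: 2 × 1.21 × (1.645 + 0.842)² = 14.96, so 15 per arm, 30 in total.
- Noncentral t, one-sided .05: 16 per arm, 32 in total (power 0.807).
- That result divided by the Wilcoxon efficiency 0.955: 16/0.955 = 16.75, so 17 per arm, 34 in total. This matches.
- One-sided .025: 19 per arm (38) by the normal formula, 21 per arm (42) by noncentral t. Neither matches.

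So 34 follows from the SCARF inputs alone and is consistent with one-sided .05. No narcotic quantity enters it.

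**2. SCARF power at 17 per arm.** Noncentrality = (1/1.1)/√(2/17) = 0.909/0.343 = 2.65, with 32 degrees of freedom.
- One-sided .05: 0.829.
- One-sided .025: 0.729.

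**3. Ceiling on the joint claim.** Success on both outcomes is a subset of success on SCARF. Joint power is therefore at most 0.829 (or 0.729), whatever the narcotic margin.

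**4. Joint power under assumed narcotic margins.** One-sided .05, 17 per arm. Narcotic power uses the same noncentral t, with noncentrality (margin in SD)/√(2/17). At correlation 0, joint power is the product, for example 0.829 × 0.829 = 0.687. At other correlations it is the bivariate normal probability with the same two marginal powers.

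| Assumed narcotic margin | Narcotic power alone | Joint, corr. 0 | Joint, corr. 0.5 | Joint, corr. 0.8 |
|---|---|---|---|---|
| 0.5 SD | 0.414 | 0.343 | 0.390 | 0.411 |
| 0.909 SD (the SCARF ratio 1/1.1) | 0.829 | 0.687 | 0.727 | 0.764 |
| 1.0 SD | 0.887 | 0.735 | 0.767 | 0.797 |
| 1.2 SD | 0.962 | 0.797 | 0.812 | 0.824 |

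**5. What the listed test can say about narcotic use.** The 95% CI half-width is t₀.₉₇₅,₃₂ × √(2/17) = 2.037 × 0.343 = 0.70 SD. As illustration only, a two-sided t-test at .05 is non-significant in 71% of trials if narcotic use is truly 0.5 SD higher with the liposomal block, and in 38% if it is 0.8 SD higher.

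**The case against.** Four points can be made for the plan.

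- **SCARF may be meant as the sole criterion.** Section IV.F can be read that way, and the plan nowhere states formally that both outcomes must succeed; that rule is inferred from the word *both*. This is fair. But if SCARF alone decides, section IV.F conflicts with sections I, II and IV.A. If either outcome could suffice, the plan would lack type I error control (1 − 0.95² = 9.75% for two independent tests at .05). Each reading calls for reconciliation.
- **A shortfall in power has not been shown.** A reader might infer that the trial misses 80% for the joint claim. The documents do not support that at one-sided .05. With a loose narcotic margin of 1.2 SD, joint power is about 80% to 82%. SCARF includes a pain item, so some positive correlation with narcotic use is plausible and zero correlation may be pessimistic.
- **Narcotic use is not without any rule.** A reader might infer that it can neither succeed nor fail. In fact the difference test can show higher use, so it can fail. Only a rule for success is absent.
- **Its measurement is partly defined.** Daily equi-analgesic dose per subject is specified, and follow-up is bounded: "Subjects will be followed for 28 days or until discharged from the hospital, whichever comes first". How daily values become one value per patient is left open, but that is equally true of SCARF and does not separate the two outcomes.

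These points limit the claim to what is stated in the verdict. None supplies the missing narcotic margin.

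**Conclusion.** The concern holds in this form: the plan has no criterion by which narcotic use, a named primary outcome, could be found comparable, and its power statement applies to SCARF alone. For the joint claim, 80% is not established. That is different from saying it is missed, because joint power depends on a narcotic margin and correlation that the documents do not give.

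Joint power cannot exceed 83% at one-sided .05 or 73% at one-sided .025. At the second level 80% would be out of reach under any margin, but the protocol does not state the level and the 34 reproduces at the first. Among the margins examined at one-sided .05, only the loosest, 1.2 SD, reaches about 80% across correlations from 0 to 0.8. All of this assumes 17 per arm, true differences of 0, SD 1.1 for the SCARF value analysed, and no dropout.

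This must be fixed, because a success rule for a primary outcome cannot credibly be added once unblinded results are known.

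**What to change.** Reconcile sections I, II, IV.A and IV.F before outcomes are examined, in one of two ways. The choice is the sponsor's.

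**(a) SCARF as the single confirmatory primary.**
- Conclude non-inferiority only if the upper confidence limit for the liposomal-minus-catheter SCARF difference is below 1 point.
- State the one-sided level. One-sided .05 is consistent with N = 34; if one-sided .025 is used, restate power as about 73%.
- Make narcotic use a key secondary, reported as the between-arm difference in mean daily equi-analgesic dose with a 95% CI (half-width about 0.70 SD).
- State that a non-significant difference will not be read as comparable.
- Remove *both* from the hypothesis.

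Cost: text changes through a protocol amendment with matching registration, no extra patients at the current N, and a claim narrowed to SCARF.

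**(b) Keep both outcomes.**
- Pre-specify and justify a narcotic margin.
- Require both upper confidence limits to fall below their margins. No alpha split is needed, because both must succeed.
- Restate the joint power at N = 34 with its assumed margin, SD and correlation.

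Cost: also an amendment, and a less favourable power figure for most margins. If the sponsor then wanted 80% joint power at one-sided .05 and correlation 0, the total would be 42 at a margin of 0.909 SD or 102 at 0.5 SD. These are examples only, since the documents give no margin.

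### A preoperative SCARF score, pre-specified as the one covariate in the primary comparison, would be a cheap gain in precision that the plan leaves unused

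*Combined protocol and SAP*

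**What the plan says.** - **Outcome (Section IV.A).** "Pulmonary function will be measured using the Standardized Assessment of Respiratory Function (SCARF) score, measured at 10 am daily". The section names no first day and no baseline or preoperative value.
- **Allocation (Section IV.C).** "Randomization will be accomplished using a standard function in Microsoft Excel that randomly chooses either the number 0 or 1". The assignment is made before the operation. No blocking or stratification is described.
- **Pre-existing catheters (Section IV.C).** For patients who arrive at surgery with a catheter, "the presence of a pre-existing pain catheter will be noted in the data collection sheet". The section describes such catheters as occasional. Section IV.F gives the flag no role.
- **Analysis (Section IV.F).** The rule for normal data opens "Normally distributed continuous variables will be compared using the", and the test it names is Student's t. Skewed data go to a Wilcoxon test, and categories to a chi-squared or Fisher test. No covariate, change score or adjusted model is named.
- **Margin and size (Section IV.F).** The margin is given as follows: "Inferiority of liposomal bupivacaine as compared to pain catheter will be defined as median daily SCARF score one point higher". The planning SD, 1.1, comes from the hospital's own intensive-care experience with this injury. From these two figures the section reaches its target: "Using beta = 0.80 and alpha = .05, this returns a total sample size of 34 subjects". It does not say whether alpha is one-sided or two-sided.

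**The concern.** The trial is small, and its conclusion rests on where a confidence bound falls against a one-point margin on a four-item score. Patients already have painful rib fractures when they are allocated. Pain, spirometry, cough and respiratory rate before surgery may well predict the same items afterwards. If they do, adjusting for the preoperative score removes variance that the t-test or Wilcoxon test leaves in, and no extra patients are needed. At about 24 eligible operations a year (Section IV.F), precision gained this way is easier to come by than precision from more recruitment.

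The trial is also unblinded (Section IV.E). An adjustment chosen after the data are seen would carry little weight, so it has to be specified beforehand.

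**Working it through.** **Inputs from the plan.** Margin 1 point, SD 1.1, total 34 (taken as 17 per arm), alpha .05. The stated beta of 0.80 is read as 80% power. The true difference is taken as 0. Sidedness is not stated, so one-sided .05 and one-sided .025 (the upper limit of a two-sided 95% interval) are both shown.

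**Input not in the plan.** The correlation ρ between preoperative SCARF and the postoperative summary. It is assumed, over 0 to 0.7.

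**1. The plan's own figure.** The normal approximation at one-sided .05 gives n per arm = 2 × [1.1 × (1.645 + 0.842) / 1]² = 14.96, so 15 per arm and 30 in total. The noncentral t gives 16 per arm, 32 in total. Dividing 16 by the Wilcoxon efficiency of 0.955 gives 16.75, so 17 per arm and 34 in total. At one-sided .025 the totals are 38 (normal) and 42 (noncentral t). The stated 34 therefore fits an unadjusted one-sided .05 comparison.

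**2. Power of the unadjusted test.** Standard error = 1.1 × √(2/17) = 0.377. Noncentrality = 1/0.377 = 2.65 on 32 degrees of freedom. Power is 82.9% at one-sided .05 and 72.9% at one-sided .025.

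**3. Power with preoperative SCARF as the single covariate.** The residual SD is 1.1 × √(1 − ρ²), on 31 degrees of freedom. Chance imbalance in the covariate inflates the variance of the adjusted difference on average by 1 + k/(N − k − 3). With k = 1 and N = 34 this is 1 + 1/30 = 1.033. At ρ = 0.5, for example, the residual SD is 1.1 × √0.75 = 0.953, the standard error is 0.953 × √(2/17 × 1.033) = 0.332, and the noncentrality is 3.01.

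| ρ (assumed) | One-sided .05 | One-sided .025 |
|---|---|---|
| unadjusted | 82.9% | 72.9% |
| 0 | 81.7% | 71.4% |
| 0.2 | 83.1% | 73.2% |
| 0.3 | 84.8% | 75.4% |
| 0.5 | 90.3% | 83.1% |
| 0.7 | 97.3% | 94.2% |

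**4. Adding the catheter flag as a second covariate.** With k = 2 the inflation is 1 + 2/29 = 1.069, on 30 degrees of freedom. Reading ρ as the multiple correlation, power at one-sided .05 is 81.9%, 83.7% and 89.4% at 0.2, 0.3 and 0.5. At 0.2 that is below the unadjusted 82.9%.

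The flag's own contribution is R² = p(1 − p)d²/1.1², for prevalence p and effect d. At an assumed prevalence of 10% and an effect of 0.5 to 1 point, R² is 0.019 to 0.074. A rare flag can easily cost more than it returns.

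**5. Chance imbalance.** In SD units, the difference in baseline means has standard error √(2/17) = 0.343. The probability that it exceeds 0.5 SD in either direction is 2 × [1 − Φ(0.5/0.343)], about 14%. At ρ = 0.5 an imbalance of 0.5 SD moves the unadjusted difference by 0.5 × 0.5 × 1.1 = 0.275 points.

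**The case against.** The strongest reply is that nothing is broken. Under randomisation the unadjusted test is valid, and 34 patients meet the 80% target at one-sided .05. The documents give no correlation, and a high one is not assured. Between the two readings the patient has rib fixation and a pleural washout, any existing catheter comes out, and a new block begins. Scores in severely injured patients may also cluster at the upper end of a 0 to 4 scale. All of this stands, and it is why the gain is shown as a range that includes zero correlation.

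A reader might infer that the plan wastes power. The documents do not support that: at a correlation of 0.2 the gain is about 0.2 points at one-sided .05.

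A reader might also infer that a damaging baseline imbalance is likely. It is not. A difference above 0.5 SD has about a 14% chance, half of that in each direction. This variation is already in the standard error and in the 83%, so the 0.275-point shift is not a further bias.

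Nor can one conclude that no preoperative SCARF is recorded. Section IV.F cites a data collection tool that is not reproduced, and daily scoring may begin before surgery. Only the absence of a defined baseline from the outcome and analysis text can be verified.

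Two practical objections also stand. Some patients may be unable to give a preoperative score, so missing baselines need a rule. And ANCOVA estimates a mean difference, whereas the margin is set on a median daily score, so adopting it changes the quantity being tested.

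**Conclusion.** The point holds as a cheap improvement. The plan defines no preoperative SCARF, gives the recorded catheter flag no analytic use, and lists only tests that take no covariates. The sample size is not wrong and the planned test is not invalid.

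The gain in power at one-sided .05 runs from nothing (a loss of about 1 point at zero correlation) through about 2 points at 0.3 and 7 points at 0.5 to 14 points at 0.7. If alpha is meant as one-sided .025, the unadjusted plan is at 72.9%, and a correlation of 0.5 would bring it to 83.1%, above the 80% target.

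These figures assume 17 per arm, complete data, a true difference of zero, a roughly continuous score analysed on the mean scale, and an SD of 1.1 that applies to the per-patient summary. The plan does not show the last of these. Simple randomisation will often give unequal arms (a 21:13 split or worse has about a 23% chance), which lowers power slightly with or without adjustment.

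**What to change.** 1. In Section IV.A, define the baseline as SCARF at the last 10 am before surgery. If the data collection tool already captures it, say so.
2. In Section IV.F, define one postoperative SCARF summary per patient. Pre-specify the primary analysis as an ANCOVA of that summary on arm and preoperative SCARF, with the one-sided confidence bound for the adjusted mean difference compared with +1. State the one-sided level.
3. State that the margin then applies to a difference in means rather than in medians.
4. Give a simple rule for missing baselines.
5. Use the pre-existing-catheter flag only in a sensitivity analysis.
6. Analyse narcotic use the same way, with opioid use in the preceding 24 hours as its baseline if the chart provides it.

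**Cost.** One bedside score and one chart extraction per patient, some missing baselines, a short addition to Sections IV.A and IV.F, and about 1 to 1.5 points of power if the correlation is zero. No extra patients are needed.

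### An unrestricted 0/1 draw leaves the split of 34 patients to chance; the average cost is about 1 point of power, and a restricted 1:1 list would avoid it almost free

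*Combined protocol and SAP*

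**What the plan says.** Section IV.C (Study Design and Research Methods) describes allocation in one sentence: an Excel function that "randomly chooses either the number 0 or 1". Section IV.A says only that "Individuals undergoing SSRF will be randomized to two treatment arms". No section gives an allocation ratio, blocks, strata or a list prepared in advance, so as written this is simple randomization.

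Section IV.F (Data Analysis Plan) sets the non-inferiority margin as a "median daily SCARF score one point higher", takes an SD of 1.1, and states "Using beta = 0.80 and alpha = .05"; "this returns a total sample size of 34 subjects". It expects enrolment to take 1.5 years. It gives no target per arm, no sidedness and no allowance for unequal arms or dropout. Section IV.E says that providers, patients and the research coordinator will all know the assignment.

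**The concern.** A two-group comparison of fixed total size is most precise when the groups are equal. Independent 0/1 draws do not enforce equality, and with only 34 patients a visible imbalance is common. Two things are at stake.

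- **Precision.** The total of 34 carries little reserve above 80% power, and an unequal split uses up part of it.
- **Balance over calendar time.** If one arm is filled mainly early and the other mainly late, any drift in care over 1.5 years is partly confounded with treatment. The planned two-group tests do not adjust for calendar time.

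Both can be limited in the same software, without more patients or visits. This point concerns balance only. Who holds the sequence is a separate matter, except where it affects the choice of fix.

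**Working it through.** **Inputs from the plan.** Total N = 34, margin 1 point, SD 1.1, alpha .05 and 80% power (the plan writes 0.80 as beta; I read it as power), all from section IV.F. Section IV.F names a t-test or a Wilcoxon test, depending on a normality check.

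**Assumptions not in the plan.** Independent draws with probability 0.5, true difference 0, no dropout, enrolment stopping at 34, and a one-sided .05 test.

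**Step 1: reproduce the plan's figure.**
- Normal approximation, one-sided .05: 2 × [1.1 × (1.645 + 0.842)]² = 14.96, so 15 per arm, 30 in total.
- Noncentral t, one-sided .05: 15.68, so 16 per arm, 32 in total.
- The t result divided by the Wilcoxon relative efficiency 3/π = 0.955: 16.4, so 17 per arm, **34 in total**.
- Two-sided .05: 38 (normal) or 42 (t) in total.

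The one-sided readings fit 34 and the two-sided ones do not, so one-sided .05 is used below.

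**Step 2: distribution of the split.** The number allocated to one arm is Binomial(34, 0.5). P(17:17) = C(34,17)/2³⁴ = 2,333,606,220/17,179,869,184 = 13.6%. The tail probabilities in the table count both directions.

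**Step 3: power for each split.** SE = 1.1 × √(1/n₁ + 1/n₂), and the noncentrality is 1/SE. At 17:17, SE = 0.377 and 1/SE = 2.65; at 12:22, SE = 0.395 and 1/SE = 2.53. The Wilcoxon column multiplies the arm sizes by 0.955 in the t calculation.

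| Split | P(this or worse) | Normal | t | Wilcoxon |
|---|---|---|---|---|
| 17:17 | – | 84.3% | 82.9% | 81.2% |
| 14:20 | 39.2% | 83.3% | 81.8% | 80.2% |
| 13:21 | 22.9% | 82.4% | 81.0% | 79.3% |
| 12:22 | 12.1% | 81.3% | 79.8% | 78.1% |
| 11:23 | 5.8% | 79.8% | 78.3% | 76.6% |
| 10:24 | 2.4% | 78.0% | 76.4% | 74.6% |
| Average over draws | – | 83.3% | 81.8% | 80.2% |

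The average loss against 17:17 is about 1 point in every column. At 12:22 it is about 3 points (for t, 82.9 − 79.8 = 3.1), and at 10:24 about 6 to 7 (for t, 82.9 − 76.4 = 6.5). In patients, 12:22 is worth 4 × 12 × 22/34 = 31.1 balanced patients, a loss of about 3.

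**Step 4: balance over time.** Take the first 17 patients as the first half of enrolment.
- Simple draws: P(5:12 or worse) = 2 × Σ C(17,k)/2¹⁷ for k = 0 to 5 = 18,804/131,072 = 14.3%.
- One shuffled list of 17 zeros and 17 ones: 2 × Σ C(17,k)·C(17,17−k)/C(34,17) for k = 0 to 5 = 3.8%.

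The single list helps less early on. The first 10 patients split 3:7 or worse in 34% of trials with simple draws and in 26% with the shuffled list.

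**Step 5: price of restriction.** Someone who knows all past allocations and always guesses the arm that is behind gains, over chance, 2³³/C(34,17) − 0.5 = 3.2 correct guesses in 34 with one shuffled list. With fixed blocks of 4 the gain is 2³/C(4,2) − 0.5 = 0.83 per block, and 0.83 × 8.5 = 7.1 in 34. I have not computed the figure for randomly varying blocks.

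**The case against.** Simple randomization is valid and unbiased, and it is the hardest scheme to predict, which has real value in an open-label trial. The expected loss is about 1 point, and average power stays above 80% in all three one-sided calculations. This much stands, and it is why the point is only a cheap improvement.

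A reader might infer four stronger things that the documents do not support.

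- **That a 12:22 split takes the trial below its planned 80%.** This depends on a test and a sidedness that section IV.F does not tie to the calculation. At 12:22, power is 81.3% (normal), 79.8% (t) or 78.1% (Wilcoxon). The chance that the split alone brings power under 80% is 5.8%, 12.1% or 22.9% respectively.
- **That 34 patients suffice only if the arms are close to 17 each.** At 14:20, power is still 80.2% to 83.3%.
- **That imbalance explains a shortfall under a two-sided .05 test.** On that reading power is already 75.5% (normal) or 72.9% (t) at 17:17. That gap comes from the sample size, and balancing the arms would not close it.
- **That the time imbalance matters because the block technique is being learned.** Section IV.G describes both modalities as already used at the hospital, and no section mentions a learning period. The time argument rests on ordinary drift in care.

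**Conclusion.** The point holds as a modest, avoidable loss of precision and of balance over time. The draw in section IV.C leaves the arm sizes to chance. On the one-sided .05 reading, with true difference 0 and no dropout, the cost is about 1 point of power on average, about 3 points at 12:22 (ending at roughly 78-81%), and about 6 or more in the 2.4% of draws at 10:24 or worse. A first half of enrolment split 5:12 or worse has a 14% chance, which a shuffled 17/17 list would cut to 4%. None of this biases the comparison or invalidates the trial. The split probabilities depend only on fair, independent draws and a total of 34; the power figures also depend on the assumed sidedness, test and true difference.

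**What to change.** In section IV.C, replace the draw with a 1:1 allocation list generated before enrolment in permuted blocks of randomly varying size, used strictly in order, with the block sizes not disclosed to enrolling staff. State the allocation ratio. Blocks are preferable because they control balance throughout enrolment. A simpler alternative is one list of 17 zeros and 17 ones sorted on a random number in Excel, but it guarantees balance only at patient 34 and needs a rule for what happens if enrolment does not stop at 34.

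The cost is one or two sentences in the protocol and a few minutes' work, with no extra patients or visits. The downside is that some allocations become easier to guess in this open-label trial, so the section should also say that upcoming allocations are kept from those who enrol patients.
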